7.6.2. Instructions for Reporting Special Situations

7.6.2.1. Instructions for Reporting Pregnancies

The investigator should report all pregnancies that are identified after the subject first consents to participate in the study (ie, signs the informed consent) and throughout the study, including the post study drug follow-up period, to the Gilead DSPH using the pregnancy report form within 24 hours of becoming aware of the pregnancy. Refer to Section 7.3 and the eCRF completion guidelines for full instructions on the mechanism of pregnancy reporting.

The pregnancy itself is not considered an AE nor is an induced elective abortion to terminate a pregnancy without medical reasons.

Any premature termination of pregnancy (eg, a spontaneous abortion, an induced therapeutic abortion due to complications or other medical reasons) must be reported within 24 hours as an SAE. The underlying medical reason for this procedure should be recorded as the AE term.

A spontaneous abortion is always considered to be an SAE and will be reported as described in Sections 7.3 and 7.4. Furthermore, any SAE occurring as an adverse pregnancy outcome post study must be reported to Gilead DSPH.

The subject should receive appropriate monitoring and care until the conclusion of the pregnancy. The outcome should be reported to Gilead DSPH using the pregnancy outcome report form. If the end of the pregnancy occurs after the study has been completed, the outcome should be reported directly to Gilead DSPH. Gilead DSPH contact information is as follows:
Email: [contact] and [contact].

Pregnancies of female partners of male study subjects exposed to Gilead or other study drugs must also be reported and relevant information should be submitted to Gilead DSPH using the pregnancy and pregnancy outcome forms within 24 hours. Monitoring of the subject should continue until the conclusion of the pregnancy. If the end of the pregnancy occurs after the study has been completed, the outcome should be reported directly to Gilead DSPH, [contact] or email [contact].

Clinical staff should also report any relevant pregnancies to the Ribavirin Pregnancy Registry at [name] (see also <http://www.ribavirinpregnancyregistry.com>).

Refer to [Appendix 2](#) for Pregnancy Precautions, Definition for Female of Childbearing Potential, and Contraceptive Requirements.

7.6.2.2. Reporting Other Special Situations

All other special situation reports must be reported on the special situations report form and forwarded to Gilead DSPH within 24 hours of the investigator becoming aware of the situation. These reports must consist of situations that involve study IMP and/or Gilead concomitant medications, but do not apply to non-Gilead concomitant medications.

Special situations involving non-Gilead concomitant medications does not need to be reported on the special situations report form; however, for special situations that result in AEs due to a non-Gilead concomitant medication, the AE should be reported on the AE form.

Any inappropriate use of medications prohibited by this protocol should not be reported as “misuse,” but may be more appropriately documented as a protocol deviation.

Refer to Section 7.3 and the eCRF completion guidelines for full instructions on the mechanism of special situations reporting.

All clinical sequelae in relation to these special situation reports will be reported as AEs or SAEs at the same time using the AE eCRF and/or the SAE report form. Details of the symptoms and signs, clinical management, and outcome will be reported, when available.

8. STATISTICAL CONSIDERATIONS

8.1. Analysis Objectives and Endpoints

8.1.1. Analysis Objectives

The primary objectives of this study are as follows:

- To evaluate the safety of sofosbuvir (SOF) 200 mg or 400 mg + ribavirin (RBV) for 24 weeks and LDV/SOF for 12 weeks as assessed by review of the accumulated safety data in each treatment arm
- To evaluate the efficacy of sofosbuvir (SOF) 200 mg or 400 mg + ribavirin (RBV) for 24 weeks and LDV/SOF for 12 weeks measured by the proportion of subjects with renal insufficiency who have achieved a sustained viral response 12 weeks after treatment discontinuation (SVR12) in each treatment arm
- To evaluate the steady state pharmacokinetics of SOF and its metabolites and LDV upon dosing SOF 200 mg or 400 mg or LDV/SOF in subjects with renal insufficiency

The secondary objectives of this study are as follows:

- To evaluate the proportion of subjects with renal insufficiency who attain SVR at 4 and 24 weeks after discontinuation of treatment (SVR4 and SVR24)
- To evaluate the kinetics of plasma HCV RNA during and after treatment discontinuation
- To evaluate the emergence of viral resistance to SOF and LDV during and after treatment discontinuation

The exploratory objective of this study is:

PPD

8.1.2. Primary Endpoint

The primary safety endpoints include incidences of AEs, laboratory, 12-lead ECG, and vital sign abnormalities.

The primary PK endpoints are parameters AUC_{τ} , C_{\max} , and C_{τ} for analytes SOF, its metabolites, LDV and RBV as applicable.

The primary efficacy endpoint is SVR12 (HCV RNA < LLOQ 12 weeks after discontinuation of therapy).

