8.5. Safety Analysis

Safety will be evaluated by assessment of clinical laboratory tests, physical examinations, vital signs measurements, at various time points during the study, and by the documentation of AEs.

All safety data collected on or after the first dose of study drug administration up to 30 days after the last dose of study drug will be summarized according to the study drug received. Safety endpoints will be summarized as the number (proportion) of subjects with events or abnormalities for categorical data or as an 8-number summary (n, mean, standard deviation, minimum, Q1, median, Q3, maximum) for continuous data.

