7.4. Body Weight, Height, BMI and Vital Signs

Absolute value and change from baseline in vital signs (systolic blood pressure [SBP], diastolic blood pressure [DBP] and pulse) at each visit will be summarized for the Safety Analysis Set using descriptive statistics by treatment cohort for each postbaseline analysis window. In the case of multiple values in an analysis window, data will be selected for analysis as described in Section 3.8.3. No inferential statistics will be generated.

A listing of height (at screening), body weight, and BMI, and a listing of SBP, DBP, pulse, respiration and temperature will be provided.

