7.8. Changes From Protocol-Specified Safety Analyses

There are no deviations from the protocol-specified safety analyses.

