15.11.2.2.1	Grade 3 or 4 Treatment-Emergent Adverse Events	Safety Analysis Set
15.11.2.2.2	Grade 2, 3, or 4 Treatment-Emergent Adverse Events	Safety Analysis Set
15.11.2.3.1	Treatment-Emergent Treatment-Related Adverse Events	Safety Analysis Set
15.11.2.3.2	Treatment-Emergent Treatment-Related Adverse Events by Preferred Term	Safety Analysis Set
15.11.2.3.3	Grade 3 or 4 Treatment-Emergent Treatment-Related Adverse Events	Safety Analysis Set
15.11.2.3.4	Grade 2, 3, or 4 Treatment-Emergent Treatment-Related Adverse Events	Safety Analysis Set
15.11.4.1	Treatment-Emergent Serious Adverse Events	Safety Analysis Set
15.11.4.3	Treatment-Emergent Treatment-Related Serious Adverse Events	Safety Analysis Set
15.11.5.1	Adverse Events Leading to Premature Discontinuation of Study Drug	Safety Analysis Set
15.11.5.2	Adverse Events Leading or Interruption of Study Drug	Safety Analysis Set
15.11.6.1.1	Hemoglobin (g/dL) and Change from Baseline by Visit	Safety Analysis Set
15.11.6.1.2	Subjects with Postbaseline Hemoglobin < 10 g/dL and < 8.5 g/dL	Safety Analysis Set
15.11.6.1.3	Reticulocytes (x10 ³ /uL) and Change from Baseline by Visit	Safety Analysis Set
15.11.6.1.4	WBC (x10 ³ /uL) and Change from Baseline by Visit	Safety Analysis Set
15.11.6.1.5	Neutrophils (x10 ³ /uL) and Change from Baseline by Visit	Safety Analysis Set
15.11.6.1.6	Lymphocytes (x10 ³ /uL) and Change from Baseline by Visit	Safety Analysis Set
15.11.6.1.7	Platelets (x10 ³ /uL) and Change from Baseline by Visit	Safety Analysis Set
15.11.6.2.1	ALT (U/L) and Change from Baseline by Visit	Safety Analysis Set
15.11.6.2.2	AST (U/L) and Change from Baseline by Visit	Safety Analysis Set
15.11.6.2.3	Total Bilirubin (mg/dL) and Change from Baseline by Visit	Safety Analysis Set
15.11.6.2.4	Alkaline Phosphatase (U/L) and Change from Baseline by Visit	Safety Analysis Set
15.11.6.2.5	Creatinine (mg/dL) and Change from Baseline by Visit	Safety Analysis Set
15.11.6.2.6	Estimated Glomerular Filtration Rate by Cockcroft-Gault (mL/min) and Change from Baseline by Visit	Safety Analysis Set
15.11.6.3	INR and Change from Baseline by Visit	Safety Analysis Set
15.11.6.4.1	Treatment-Emergent Graded Laboratory Abnormalities	Safety Analysis Set
15.11.6.4.2	Treatment-Emergent Grade 3 or 4 Laboratory Abnormalities	Safety Analysis Set
15.11.7.1.1	Systolic Blood Pressure (mmHg) and Change from Baseline by Visit	Safety Analysis Set
15.11.7.1.2	Diastolic Blood Pressure (mmHg) and Change from Baseline by Visit	Safety Analysis Set

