15.11.7.1.3	Pulse (bpm) and Change from Baseline by Visit	Safety Analysis Set
15.11.7.3	Concomitant Medications	Safety Analysis Set

Table Number	Title	Analysis Set
15.11.9.1	Summary of On-Treatment ECG Abnormality	Safety Analysis Set
15.11.9.2.1	PR Interval (ms) and Change from Baseline by Visit	Safety Analysis Set
15.11.9.2.2	QRS Interval (ms) and Change from Baseline by Visit	Safety Analysis Set
15.11.9.2.3	QT Interval (ms) and Change from Baseline by Visit	Safety Analysis Set
15.11.9.2.4	QTcF (ms) and Change from Baseline by Visit	Safety Analysis Set
15.11.10.1.1	Echocardiogram: Ejection Fraction (%) and Change from Baseline by Visit	Safety Analysis Set
15.11.10.1.2	Echocardiogram: Fractional Shortening (%) and Change from Baseline by Visit	Safety Analysis Set
15.11.10.2.1	Echocardiogram: LVEDV (mL) and Change from Baseline by Visit	Safety Analysis Set
15.11.10.2.2	Echocardiogram: LVIDd (cm) and Change from Baseline by Visit	Safety Analysis Set
15.11.10.3	Echocardiogram: Shift Table of Baseline versus On-Treatment Diastolic Function Score Assessment by Visit	Safety Analysis Set

Figure Number	Title	Analysis Set
15.8.1	Subject Disposition	Screened Subjects
15.9.2.3	Proportion of Subjects with SVR (HCV RNA < LLOQ) by Posttreatment Visit	Full Analysis Set
15.9.2.4	Proportion of Subjects with HCV RNA < LLOQ While on Treatment by Visit	Full Analysis Set
15.10.1.1.1	Mean (SD) Plasma Concentration - Time (0 hour - 12 hours) Profiles by Visit	SOF PK Analysis Set
15.10.1.1.2	Mean (SD) Plasma Concentration - Time (0 hour - 12 hours) Profiles by Visit	GS-566500 PK Analysis Set
15.10.1.1.3	Mean (SD) Plasma Concentration - Time (0 hour - 12 hours) Profiles by Visit	GS-331007 PK Analysis Set
15.10.1.1.4	Mean (SD) Plasma Concentration - Time (0 hour - 12 hours) Profiles by Visit	LDV PK Analysis Set
15.10.1.1.5	Median (Q1, Q3) Plasma Concentration - Time (0 hour - 12 hours) Profiles by Visit	SOF PK Analysis Set
15.10.1.1.6	Median (Q1, Q3) Plasma Concentration - Time (0 hour - 12 hours) Profiles by Visit	GS-566500 PK Analysis Set
15.10.1.1.7	Median (Q1, Q3) Plasma Concentration - Time (0 hour - 12 hours) Profiles by Visit	GS-331007 PK Analysis Set
15.10.1.1.8	Median (Q1, Q3) Plasma Concentration - Time (0 hour - 12 hours) Profiles by Visit	LDV PK Analysis Set

Listing Number	Title	Analysis Set
16.1.6	Lot Number and Kit ID	Safety Analysis Set
16.2.1.3	Subject Disposition	Safety Analysis Set
16.2.1.4	Reasons for Screen Failure	Subjects Screened But Not Enrolled

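### The incidence of vital-sign abnormalities is a primary safety endpoint in the protocol, but the Cohort 3 SAP plans no subject count for it and declares no deviation

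*Protocol*

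**What the plan says.** Protocol section 8.1.2 gives four components: "The primary safety endpoints include incidences of AEs, laboratory, 12-lead ECG, and vital sign abnormalities". Protocol section 8.5 says that safety endpoints are summarized "as the number (proportion) of subjects with events or abnormalities for categorical data or as an 8-number summary", the latter for continuous data.

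SAP section 7.4 plans summaries of "Absolute value and change from baseline in vital signs (systolic blood pressure [SBP], diastolic blood pressure [DBP] and pulse) at each visit". It adds that "a listing of SBP, DBP, pulse, respiration and temperature will be provided". Appendix 2 of the SAP carries this through. Table 15.11.7.1.1 is titled "Systolic Blood Pressure (mmHg) and Change from Baseline by Visit", Tables 15.11.7.1.2 and 15.11.7.1.3 do the same for diastolic pressure and pulse, and Listing 16.2.8.2.1 holds the individual values. No other table, figure or listing concerns blood pressure, pulse, respiration or temperature.

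SAP section 7.8 then states: "There are no deviations from the protocol-specified safety analyses".

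**The concern.** An incidence is a number of subjects out of those at risk. By-visit means, quartiles and changes are not that quantity and cannot be turned into it. A report that follows the SAP to the letter would therefore give no number or percentage for one of the four components that the protocol calls primary for safety. A reader of SAP 7.8 would have no warning of this.

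Neither the protocol's statistical section nor the SAP says what counts as a vital-sign abnormality for this endpoint. Anyone asked for the count later would have to choose limits after seeing the values, in an open-label cohort.

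**Working it through.** The plan states no figure for this endpoint, so the check is a trace of each named component, followed by a test of whether the missing count could be obtained another way.

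**Step 1. Trace the four components.**

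| Component in protocol 8.1.2 | SAP text | Subject count in SAP Appendix 2 |
|---|---|---|
| AEs | 7.1.6: number and percentage by SOC and PT | Yes: 15.11.2.1.2 and related tables |
| Laboratory | 7.2.2: treatment-emergent grades, counted by worst grade | Yes: 15.11.6.4.1 ("Treatment-Emergent Graded Laboratory Abnormalities") and 15.11.6.4.2 |
| 12-lead ECG | 7.5: value and change, plus listings; no count described | By title only: 15.11.9.1 ("Summary of On-Treatment ECG Abnormality") |
| Vital signs | 7.4: value and change, plus listings; no count described | None |

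**Step 2. Can the by-visit tables supply the count?** Take systolic pressure and the Appendix 3 boundary for Grade 2, above 159 mmHg. Suppose all 15 subjects have a value at each of the 8 post-baseline windows (SAP Tables 3-1 and 3-3: Weeks 1, 2, 4, 6, 8, 10, 12 and FU-4). Suppose also that each window shows a maximum above 159 and a third quartile at or below 159.

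- With the third quartile as the 12th of 15 ordered values, between 1 and 15 − 12 = 3 subjects exceed 159 at each window.
- If it is the same subject each time, the total is 1 subject.
- If the subjects differ, up to 8 × 3 = 24 high readings are available, enough to cover all 15.

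The same table is thus compatible with anything from 1/15 (6.7%) to 15/15 (100%). These are logical limits, not a forecast. Value and change are also summarized separately, so the table does not show whether a subject with a high reading had moved up a grade from that subject's own baseline.

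**Step 3. Can the listing supply it?** Yes, by hand, once limits are chosen. With baseline there are 9 windows. For systolic pressure, diastolic pressure and temperature, that is 15 × 9 × 3 = 405 scheduled values at most. For all five listed parameters it is 15 × 9 × 5 = 675. A post-treatment Week 4 visit may fall 7 days late, at day 35, while the vital-sign window closes at day 30, so some visits will drop out.

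**Step 4. Are limits available in the protocol?** In part. Appendix 3 has numeric cut-offs for hypertension in Grades 1 to 3 (starting at 140 systolic or 90 diastolic, then above 159 or 99, then above 179 or 109) and for fever. Hypertension Grade 4 is defined by clinical consequences, and hypotension by symptoms and treatment. Pulse and respiratory rate have no measurement cut-off. The SAP applies the scale to laboratory values and AEs, not to vital-sign readings.

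**Step 5. Do the AE tables supply it?** In part. Protocol 7.1.3 requires an abnormal vital sign to be recorded as an AE when it comes with signs or symptoms and meets the AE definition. Symptom-free readings may or may not be reported, depending on the investigator's judgment under 7.1.1.

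**Step 6. What could the count show?** Little. With 15 subjects, an observed count of 0 has an exact two-sided 95% upper limit of 1 − 0.025^(1/15) = 21.8%.

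**The case against.** The strongest reply is that the SAP does what the protocol's analysis section asks. Protocol 8.5 speaks of vital-sign measurements and permits an 8-number summary for continuous data. Sections 8.5.2 and 8.5.3 require counts for AEs and laboratory abnormalities, and no section sets out a vital-sign abnormality analysis. On that reading the loose end lies inside the protocol, between 8.1.2 and 8.5, and SAP 7.8 is literally true.

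Part of this stands. The by-visit summaries fit the general rule in 8.5 and should stay, and the protocol never defines the term. A reader might infer that SAP 7.4 breaches protocol 8.5, or that a change was concealed. The documents do not support either. What does not stand is the step from a permitted summary to a reported endpoint. Section 8.1.2 names an incidence, the same sentence of 8.5 assigns a number and proportion of subjects to abnormalities, and a mean or quartile by visit is neither.

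A second reply is that AE tables and the listing already cover the matter. They narrow the gap to readings not reported as AEs, and they mean that nothing is hidden. They do not close it, because 8.1.2 names vital-sign abnormalities separately from AEs.

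A reader might also infer that the ECG component is fully specified and vital signs alone were left behind. The documents do not support that contrast. SAP 7.5 describes no ECG count, and only the title of Table 15.11.9.1 suggests one. The firm comparison is with AEs and laboratory data.

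**Conclusion.** The point holds and is minor. One named primary safety component has no planned subject count in the Cohort 3 SAP, and the blanket statement in SAP 7.8 is not accurate for that component. This rests on reading incidence as a number of subjects and on taking Appendix 2 as the full list of planned outputs.

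The effect is small. There is no comparison group, no hypothesis test and no sample-size calculation to disturb. A reader might infer that abnormal vital signs would go unseen or that the trial's safety conclusions are unsound. Neither follows, given the listing, the by-visit extremes for blood pressure and pulse, and AE reporting. Nothing can be said about Cohorts 1 and 2, whose separate SAP is not among the documents.

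**What to change.** Before SVR12 database finalization, add one table to SAP 7.4 in the form of the laboratory abnormality table:

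- **Content:** number and percentage of Safety Analysis Set subjects whose worst post-baseline grade, from first dose through last dose plus 30 days, is at least one grade above baseline, shown by maximum grade.
- **Cut-offs:** the numeric hypertension cut-offs (Grades 1 to 3) and the fever cut-offs in protocol Appendix 3.
- **Footnote:** single readings are used, although Appendix 3 calls for repeat testing at the same visit for hypertension. The fever cut-offs are for non-axillary temperature.
- **SAP 7.8:** name pulse, respiratory rate and low blood pressure as having no numeric cut-off and being reported by descriptive statistics and/or listing only.

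If the sponsor wants no count at all, SAP 7.8 should say that statistics and a listing replace this component. If the SAP is already final, its introduction sends later changes to the CSR.

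The cost is one table, one footnote and one sentence, with no new data. The downside is that visit-to-visit variation in blood pressure will push some stable subjects up a grade. This is expected mostly at low grades, though the documents give no variability from which to estimate how often. With 15 subjects each one moves the percentage by 6.7 points, so the table should be read grade by grade and not as a single total.

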8.1.3. Secondary Endpoint

Secondary PK endpoints are parameters AUC_{last} , C_{last} , T_{max} , T_{last} , λ_z , and $t_{1/2}$ for analytes SOF, its metabolites, LDV and RBV as applicable.

Secondary efficacy endpoints include the proportion of subjects with SVR4 and SVR24, the proportion of subjects with virologic failure including viral breakthrough and relapse.

8.1.4. Other Endpoints of Interest

Additional efficacy evaluations may include HCV RNA change from baseline; ALT normalization, and viral kinetic parameters.

8.2. Analysis Conventions

All individual subject data will be listed as measured. All statistical summaries and analyses will be performed using SAS® software (SAS Institute, Cary, North Carolina, USA).

The study drugs in this study include SOF, RBV and LDV/SOF. Last dose of study drug refers to the last dose of any of the study drugs in a treatment group and will be used in the definition of treatment-emergent AEs and laboratory abnormalities as well as the efficacy endpoints of SVR at various post-treatment time points.

All analyses will be presented by treatment cohort. Subjects who receive study drug other than that to which they were assigned will be analyzed according to the study drug received.

8.2.1. Analysis Sets

8.2.1.1. Efficacy

The analysis set for antiviral activity analyses will be the Full Analysis Set (FAS) which includes subjects who were enrolled and received at least one dose of study drug.

8.2.1.2. Safety

The primary analysis set for safety analyses will be the Safety Analysis Set which includes subjects who received at least one dose of study drug.

Treatment-emergent data will be analyzed and defined as data collected from the first dose of study drug through the date of the last dose of study drug plus 30 days.

8.2.1.3. Pharmacokinetics

The PK analysis set will include all subjects who are enrolled and have received at least one dose of study drug and for whom PK concentration data of interested analytes (SOF, its metabolites, LDV or RBV) are available. The PK analysis set will be used for analyses of general PK.

8.2.2. Data Handling Conventions

Missing data can have an impact upon the interpretation of the trial data. In general, values for missing data will not be imputed.

For the analysis of post-baseline categorical efficacy endpoints, if a data point is missing and is immediately preceded and followed in time by values that are deemed successes, then the missing data point will be termed a success; otherwise the data point will be termed a failure.

Any subject with missing data due to premature discontinuation of the study medication will be considered a failure at the time points on, or following, the date of discontinuation. If no HCV RNA values are obtained after the last dose of study medication, the subject will be considered a treatment failure for the SVR endpoints.

Where appropriate, safety data for subjects that did not complete the study will be included in summary statistics. For example,

- If a subject received study medication, the subject will be included in a summary of adverse events according to the treatment received; otherwise, if the subject is not dosed then they will be excluded from the summary.
- If safety laboratory results for a subject are missing for any reason at a time point, the subject will be excluded from the calculation of summary statistics for that time point. If the subject is missing a predose value, then the subject will be excluded from the calculation of summary statistics for the predose value and the change from predose values.

Values for missing safety laboratory data will not be imputed; however, a missing baseline result will be replaced with a screening result, if available. If no pretreatment laboratory value is available, the baseline value will be assumed to be normal (i.e., no grade [Grade 0]) for the summary of graded laboratory abnormalities.

Values for missing vital signs data will not be imputed; however, a missing baseline result will be replaced with a screening result, if available.

HCV RNA values below the LLOQ for the assay will be set to the lower limit minus 1 for calculation of summary statistics for the actual HCV RNA values and the change from baseline values by study visit. The reported values will be provided in the HCV RNA listing.

For selected analyses of early time point data, HCV RNA data (IU/mL) may be transformed to the logarithmic (base 10) scale (\log_{10} IU/mL).

PK concentration values below the lower limit of quantitation (BLQ) will be treated as zero for determination of summary and order statistics. Individual values that are BLQ will be presented as “BLQ” in the concentration data listing. For the presentation of summary and order statistics, if at least 1 subject has a concentration value BLQ for the time point, then the minimum value will be displayed as “BLQ.” If more than 50% of the subjects have a concentration data value

BLQ for the time point, then the minimum and median values will be displayed as “BLQ.” If more than 75% of the subjects have a concentration data value of BLQ for a given time point, then the minimum, 1st quartile [q1], median, and 3rd quartile [Q3] values will be displayed as “BLQ.” If all subjects have concentration data values BLQ for the time point, then all order statistics (minimum, first quartile [Q1], median, third quartile [Q3], maximum) will be displayed as “BLQ”.

Exposure parameters that are selected for statistical analysis will be natural log-transformed. Concentration values that are BLQ will be excluded for any ratio or natural log-transformed statistical analysis.

